The primary objective of the trial is to evaluate the safety and tolerability of combined pembrolizumab and vorinostat therapy in subjects with relapsed or refractory DLBCL, FL, or HL. The dose escalation portion of the study will evaluate the safety and tolerability of the study regimen, establish the maximum tolerated dose (MTD), and determine the recommended Phase II dose (RP2D). Through the expansion cohort, we will obtain additional safety information, including information about any delayed toxicities, and we will obtain a preliminary estimate of the efficacy of the combination in subjects with relapsed or refractory DLBCL, FL, or HL, as assessed by the overall response rate (ORR). The complete response (CR) rate, duration of response (DOR), overall survival (OS) and progression-free survival (PFS) will also be studied. Response assessments will be

performed by investigators using the 2014 Lugano Classification and as a secondary endpoint we will evaluate the responses according to the LYRIC criteria. Immunologic and genomic biomarkers of response and resistance to study therapy will be explored.

Endpoints:

- Primary Endpoint: Toxicity
- Secondary Endpoints: Overall response rate (ORR), complete response (CR) rate, time to response (TTR), duration of response (DOR), overall survival (OS) and progression free survival (PFS).

Sample Size/Number of Trial Subjects:

Expected sample size will be 52 evaluable patients (12 in the dose-escalation portion of the study, and 40 in the expansion cohort). The minimum sample size is 6 evaluable patients. Considering replacement of inevaluable patients, the maximum study accrual is set at 60 patients.

Estimated Duration of the Study

Estimated Enrollment Period: 48 months

Estimated Duration of Trial: 72 months

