4.4.7 Immune-Related Adverse Events

An irAE is defined as a clinically significant AE of any organ that is associated with study drug exposure, is of unknown etiology, and is consistent with an immune-related mechanism. AEOSI data for melanoma and lung subjects demonstrates that irAEs were reported in 16.1% of subjects (251 of 1562) overall; AEOSI were considered by the Investigators to be drug related in 14.3% of subjects (223 of 1562). The majority of AEOSI were Grade 1 or 2 in

severity. Overall, serious AEOSI occurred in 4.2% of subjects at 2 mg/kg Q3W, 3.7% of subjects at 10 mg/kg Q3W, and 3.9% of subjects at 10 mg/kg Q2W. There was one AEOSI (pneumonitis) related to death in 10 mg/kg Q3W arm, in a subject with NSCLC. The rate of discontinuation due to AEOSI was low (2.6%).

[figure not shown]
The most commonly reported immune-related adverse events across the dose schedules are hypothyroidism (7.2%), pneumonitis (2.9%), hyperthyroidism (2.2%), colitis (1.3%) and skin AEOSI (1.3% including all terms). Based on the mechanism of action of MK-3475 and similar immunomodulatory agents, Merck is interested in potential irAEs, and encourages appropriate investigation of signs and symptoms suggestive of these. Consultation with the appropriate medical specialist should be considered when investigating a possible irAE. These events can occur after the first dose to several months after the last dose of treatment. Mild irAEs are usually treated symptomatically and do not require dosing delays or discontinuation. Higher grade and persistent lower grade irAEs typically necessitate withholding or discontinuing treatment and administration of systemic steroids or other immunosuppressive agents (such as tumor necrosis factor blockers), when systemic steroids are not effective. Early recognition of irAEs and initiation of treatment are critical to reduce the risk of complications, since the majority of irAEs are reversible with the use of steroids and other immune suppressants.

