7.6.1.2 Pembrolizumab Dose Modification (Escalation/Titration/Other)

Note: If pembrolizumab administration is held for toxicity, and the toxicity is most likely attributed to pembrolizumab and not attributed to vorinostat, administration of vorinostat can continue.

During the Phase I portion of the study, no intrapatient dose de-escalation will be allowed during the DLT period. After the DLT period, the following dose modifications are permitted for pembrolizumab-related adverse events according the guidelines outlined below in Table 5 for pembrolizumab. If, according to Table 5, pembrolizumab is discontinued permanently, the patient should continue to receive vorinostat.

Adverse events (both non-serious and serious) associated with pembrolizumab exposure may represent an immunologic etiology. These immune-related adverse events may occur shortly after the first dose or several months after the last dose of pembrolizumab treatment and may affect more than one body system simultaneously. Therefore, early recognition and initiation of treatment is critical to reduce complications. Based on existing clinical study data, most irAEs were reversible and could be managed with interruptions of pembrolizumab, administration of corticosteroids and/or other supportive care. For suspected irAEs, ensure adequate evaluation to confirm etiology or exclude other causes. Additional procedures or tests such as bronchoscopy, endoscopy, skin biopsy may be included as part of the evaluation. Based on the severity of irAEs, withhold or permanently discontinue pembrolizumab and administer corticosteroids. Dose modification and toxicity management guidelines for irAEs associated with pembrolizumab are provided in Table 5. See Section 7.10.1 for supportive care guidelines, including use of corticosteroids.

Table 5. Dose modification and toxicity management guidelines for immune-related AEs associated with pembrolizumab

General instructions:

1. Corticosteroid taper should be initiated upon AE improving to Grade 1 or less and continue to taper over at least 4 weeks.
2. For situations where pembrolizumab has been withheld, pembrolizumab can be resumed after AE has been reduced to Grade 1 or 0 and corticosteroid has been tapered. Pembrolizumab should be permanently discontinued if AE does not resolve within 12 weeks of last dose or corticosteroids cannot be reduced to ≤ 10 mg prednisone or equivalent per day within 12 weeks.

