9.2.2 Adverse Event (AE) collection guidelines

- During Cycles 1-2, all grade toxicities with start and stop dates will be reported in the eCRFs.
- After Cycle 2 until the end of the safety follow-up period (30-days post-last dose for AE or 90 days post-last dose for SAE), the highest grade toxicity per cycle and the highest grade toxicity and all SAEs during the safety follow-up period with start/stop dates will be reported in the eCRFs.

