10.2 Endpoint Definitions

Overall Response Rate (ORR): Defined as the proportion of patients that have a documented CR or PR at any time during study treatment.

Complete Response (CR) rate: Defined as the proportion of patients that have a documented CR at any time during study treatment.

Duration of Response (DOR): Defined as the time from the first achievement of PR or CR to time of PD. Patients who never achieve PR or CR are excluded. Patient who has not had disease progression/relapse at last follow-up is censored at the time of last follow-up. If a patient receives non-protocol anti-lymphoma treatment prior to disease progression, the patient is censored at the time of non-protocol anti-lymphoma treatment.

Overall Survival: Defined as time from initiation of study therapy to death from any cause. If a patient is alive at the last evaluation time period, survival time is censored at the time of last follow-up.

Progression-Free Survival (PFS): Defined as the time from initiation of study therapy to the first observation of disease relapse/progression or death from any cause, whichever occurs first. If the patient has not progressed relapsed or died, the patient is censored at the time of last follow-up. If a patient receives non-protocol anti-lymphoma treatment prior to disease progression, the patient is censored at the time of non-protocol anti-lymphoma treatment.

Toxicity: Toxicity and adverse events will be recorded using the NCI CTCAE 4.03 scale. Observed toxicities will be summarized by type (organ affected or laboratory determination such as absolute neutrophil count), severity (by NCI CTCAE v4.03 and nadir or maximum values for lab measures), date of onset, duration, reversibility, and attribution.

Unacceptable Toxicity: defined as one of the following AEs that is at least possibly related to study treatment, at any point on study therapy:

- Any Gr 3 or higher IrAE that does not resolve to Gr ≤ 1 within 7 days with the exception of:
 - Grade 3 immune-related hepatitis if ALT or AST $< 8 \times$ ULN or total bilirubin $< 5 \times$ ULN.
 - Grade 3 asymptomatic endocrinopathy.
 - Local inflammatory response to study therapy.
- Any other Gr ≥ 4 AE with the exception of:
 - Non-clinically significant laboratory abnormalities
 - Local inflammatory response to study therapy.
- Any Gr 5 AE.

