11.2 Safety Analysis and Stopping Rules for Excessive Toxicity in the Expansion Cohort

During enrollment into the expansion cohort, toxicity information recorded will include the type, severity, and the probable association with the study regimen. Tables will be constructed to summarize the observed incidence by severity and type of toxicity.

Because of the unique immune-related adverse events (IrAEs) observed with checkpoint inhibitors, we will monitor for “unacceptable toxicity” with this new combination of drugs

(defined in [Section 10.2](#)). The expected rate of “unacceptable toxicity” should not be $\geq 33\%$. The early stopping rule for unacceptable toxicity will be assessed after enrollment of 12 patients (total, across cohorts) treated at the RP2D and will be assessed once the 12th patient has completed at least 4 cycles of therapy. If >3 “unacceptable toxicity” events occur in the first 12 patients ($\geq 33\%$) treated (across disease subtypes) at RP2D, or at a rate $\geq 33\%$ anytime thereafter at the quarterly review, accrual will be halted and a full review of these events will be performed by the City of Hope Data Safety Monitoring Committee (DSMC). Patient accrual will not resume until approved by the DSMC to do so. These rules are in addition to the quarterly review of all toxicities submitted to the City of Hope Data Safety Monitoring Committee (DSMC). Patients with ongoing toxicity will be followed until resolution or stability.

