14.4 Expedited AE Reporting Guidelines

Each adverse event will be assessed to determine if it meets the criteria for expedited reporting. Adverse event reporting is to occur according to the site's specific IRB guidelines, and as outlined in this Section.

Table 14.4 indicates what events must be reported expeditiously.

Serious Adverse Events that require expedited reporting and unanticipated problems will be reported according to the approved [City of Hope's Institutional policy](#) via electronic submission in [iRIS](#).

Table 14.4 Expedited Reporting Guidelines

Time point	What to report expeditiously
From the signing of the consent to study completion	All unanticipated problems
Screening up to Day 1 of protocol therapy	
 Pregnancy and lactation Any reason for not starting Day 1 of protocol therapy
For the time period beginning at treatment through 90 days following cessation of treatment, or 30 days following cessation of treatment if the subject initiates new anticancer therapy, whichever is earlier	
 All SAEs regardless of relationship to protocol therapy, study procedure, underlying disease or concomitant treatment. Death due to any cause other than progression of the cancer under study All AEs that meet the definition of a UP Overdose (Section 14.2.1) of either agent Pregnancies and lactation (Section 14.2.2) Abnormal liver function tests (Section 14.2.3).
For participants yet to initiate anti-cancer therapy: From Day 1 of therapy up to 120 days post-last pembrolizumab dose	Pregnancies and lactation (Section 14.2.2).
Post Safety follow-up to removal from study	All SAEs that are considered possibly, probably, or definitely related to pembrolizumab
Note: follow-up reports must be submitted for all events that require expedited reporting when the status of the event changes and until the resolution or stabilization of the event.	

- Reportable adverse events must be followed until the event is resolved, stabilized, or determined to be irreversible by the investigator; for ongoing reportable adverse events that are unrelated to protocol therapy, the follow-up period may end 90 days following cessation of treatment, or 30 days following cessation of treatment if the subject initiates new anticancer therapy, whichever is earlier.

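### The accrual-halt rule counts unacceptable toxicity only on study therapy, so an immune-related event that starts after the last dose of both agents never enters the expansion's one numeric safety trigger

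*Combined protocol and SAP*

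**What the plan says.** Section 11.2, repeated in 7.5 and the synopsis, sets one numeric rule for patients treated at the RP2D. More than 3 unacceptable-toxicity events in the first 12 patients stops accrual. After that, if the rate is 33% or more "anytime thereafter at the quarterly review, accrual will be halted and a full review of these events will be performed" by the DSMC. The first look comes once the 12th patient has completed at least 4 cycles. The section gives immune-related adverse events (irAEs) as the reason for the rule, and adds that it supplements the DSMC's quarterly review of all toxicities.

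The event is defined in 10.2 as one of a list of AEs that "is at least possibly related to study treatment, at any point on study therapy". Neither 11.2 nor any other section adds a post-treatment window to the rate.

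On the timing of irAEs, 4.4.7 states: "These events can occur after the first dose to several months after the last dose of treatment". Section 7.6.1.2 agrees: "These immune-related adverse events may occur shortly after the first dose or several months after the last dose of pembrolizumab treatment". The synopsis gives the purpose of the expansion: "Through the expansion cohort, we will obtain additional safety information, including information about any delayed toxicities".

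Collection does continue after treatment. Section 9.2.2 sets the safety follow-up at "30-days post-last dose for AE or 90 days post-last dose for SAE". Table 14.4 requires expedited SAE reporting "through 90 days following cessation of treatment, or 30 days following cessation of treatment if the subject initiates new anticancer therapy", whichever is earlier. After safety follow-up and until removal from study it still requires "All SAEs that are considered possibly, probably, or definitely related to pembrolizumab".

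**The concern.** The rule exists because of irAEs, and the protocol says that part of their risk period lies after the last dose. The definition feeding the rule ends with therapy. Read as written, a qualifying irAE that begins after both agents have stopped cannot count towards the halt, even when it has been reported as an SAE.

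Time off therapy during accrual is part of the design. Treatment is capped at 24 months, patients in complete response may stop after at least 24 weeks, and enrolment is expected to take 48 months. Many earlier patients will therefore be off therapy while others are still being enrolled. At stake is whether the only pre-specified number that stops accrual in the expansion reflects the toxicity the trial has already recorded.

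**Working it through.** **1. The plan's own boundary.** More than 3 of 12 means at least 4: 4/12 = 33.3%, which meets the 33% limit; 3/12 = 25.0% does not. The figure in 11.2 reproduces.

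**2. The passages side by side.**

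| Element | Period covered | Section |
|---|---|---|
| Halt-rule event | On study therapy only | 10.2, used in 11.2, 7.5, synopsis |
| irAE risk period | First dose to several months after last dose | 4.4.7, 7.6.1.2 |
| AE collection | To 30 days after last dose | 9.2.2 |
| SAE collection | To 90 days (30 if new anticancer therapy starts) | 9.2.2, Table 14.4 |
| Pembrolizumab-related SAEs | Until removal from study | Table 14.4 |

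The halt rule covers the shortest period of the five.

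**3. Effect of one uncounted patient.** At the first look, 3/12 (continue) becomes 4/12 (halt). For a later review, the number of patients at the RP2D is not reported. Assume 36 of the initial 42 (4.6.4) plus the 10 added, so N = 46. The boundary is ceil(0.33 × 46) = ceil(15.18) = 16. Then 15/46 = 32.6% continues and 16/46 = 34.8% halts. With 30 or 42 earlier patients the boundary is 14/40 or 18/52, and one patient is again enough at the edge.

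**4. Loss of detection.** Let the true rate be 33%, the protocol's own limit, and let a share s of qualifying events start after therapy. The documents give no value for s; 10% to 30% is an assumption. Counted rate = 0.33 × (1 − s). Exact binomial tails:

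| s | Counted rate | P(at least 4 of 12) | P(at least 16 of 46) |
|---|---|---|---|
| 0 | 33.0% | 59.7% | 45.3% |
| 10% | 29.7% | 49.8% | 27.2% |
| 20% | 26.4% | 39.5% | 13.2% |
| 30% | 23.1% | 29.3% | 4.9% |

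These are single-look probabilities. They take one counted event per patient and full follow-up. At the first look the 12th patient may have had only 4 cycles (4 × 21 = 84 days) and some patients may still be on treatment, so a large s is less plausible there than at later quarterly reviews.

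**The case against.** **Late events are not unmonitored.** A reader might infer that they escape the trial's safety assessment or its primary endpoint. The documents do not support that. Section 11.1.2 summarises toxicity without the on-therapy limit, the DSMC reviews all toxicities quarterly, and 7.13 allows early termination on the incidence or severity of adverse reactions. The delayed-toxicity aim speaks of information to be obtained, which the collected data supply. This stands, and it confines the point to the numeric trigger.

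**Not every late irAE is off therapy.** Section 7.6.1.2 has vorinostat continue after permanent discontinuation of pembrolizumab. An irAE months after the last pembrolizumab dose may therefore still count. This also stands: the gap begins only after the last dose of both agents.

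**The wording may have been meant to widen the rule.** It may have been written to reach beyond the two-cycle DLT period rather than to exclude post-treatment events. That is possible, but the text still ends with therapy, and it does not say how to treat an event between the final dose and formal discontinuation.

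**Adding events does not always mean better detection.** With an assumed on-therapy rate of 25%, post-dose events in a further 2% or 4% of patients raise P(at least 4 of 12) from 35% to 41% or 48%. A reader might take that as halts wrongly missed. The totals, 27% and 29%, are below the protocol's 33%, so these are extra halts at rates the plan accepts. They belong under cost.

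**The pooled rate and the 10 added Hodgkin patients.** A reader might infer that the rule fails this group and that it needs its own limit. Section 11.2 states that the rule pools across cohorts and disease subtypes, and nothing in the documents suggests more toxicity in this group. How the pooled rate reacts depends on the earlier affected count, which is not reported. With 36 earlier RP2D patients and a true 50% in the added group, the halt probability runs from 0–5% (5 earlier affected) to 81–91% (11 earlier affected), over assumptions from no affected patient replaced to all replaced. A separate limit of 4 in 10 would pause accrual 22% of the time at a true 25% and would miss a true 33% in 57% of cases. That is a trade-off, not an error in the plan.

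**Conclusion.** The concern holds for the event window of the halt rule and no further. On the text, qualifying irAEs that start after the last dose of both agents cannot enter the expansion's only numeric trigger, although the protocol describes that risk period and already collects most of the data. The effect can decide a borderline review by one patient. At a true 33%, the chance of reaching 4 in 12 drops by about 10 to 30 percentage points if 10% to 30% of events are post-therapy. That size rests wholly on the assumed share; the decision shift from 3/12 to 4/12 does not. Because DSMC review and the toxicity summaries still see these events, the point is minor.

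**What to change.** In 11.2, 7.5 and the synopsis, state that for the halt rule qualifying events count from first dose to 30 days after the last dose of either agent (the later of the two), and to 90 days for those collected as SAEs, or 30 days if new anticancer therapy starts, as in Table 14.4. List later pembrolizumab-related SAEs beside the rate. Define the rate as patients with at least one event over all patients treated at the RP2D; the plan now counts events and gives no later denominator. Leave the text of 10.2 unchanged, because 7.1.1 and 7.12 also use it for treatment discontinuation.

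No separate limit for the added Hodgkin patients is needed. At most, show their event count beside the pooled rate at each quarterly review.

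The cost is small. No new SAE data are required. The counted rate can only rise, so halts become somewhat more frequent, including some at true rates below 33%. Non-serious events after day 30 may still be missed under 9.2.2, although the synopsis and 2.1 describe 90 days for severe events and events of clinical interest.

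As a separate wording point, the hepatitis exemption in 10.2 joins its transaminase and bilirubin limits with an or. Read literally, a patient above one limit is exempt when below the other. That wording should be reconciled with its intended logic.

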11.3 Sample Size Accrual Rate

The expected sample size is 52 evaluable patients: 12 during the dose-escalation portion, and 40 patients in the expansion cohort. The minimum sample size is 6 evaluable patients. Patients evaluable/inevaluable for dose-escalation portion and for dose expansion cohort are defined in Section 7.4 and 11.1.3 respectively. Considering replacement of inevaluable patients, the maximum study accrual is set at 60 patients.

11.4 Correlative Studies

A non-exhaustive list of correlative studies is provided in Section 4.6.4.3 “Biomarker Research”. These studies are exploratory in nature and meant to be hypothesis-generating.

Genomic Correlative Analyses: Comprehensive genomic analyses (i.e., WES and GEP) will be performed on pre-treatment tumor samples. We will: 1) quantify and compare total exonic mutational load between responders and non-responders; 2) assess association between mutational load and PFS; 3) assess individual genetic alterations for association with response and PFS; 4) compare GEP between responders and non-responders and assess association with PFS.

Statistical Considerations: Total exonic mutational load (TEML) will be quantified for each subject using the pre-treatment samples; these measures will be summarized within and across histology-based cohorts. Wilcoxon rank sum tests will be used to compare TEML levels between two groups, and Fisher exact tests to compare incidence of specific mutations between groups. In addition, logistic regression models will be used to evaluate the influence of TEML on whether or not patients responded to therapy. For HL patients, we will evaluate influence of TEML on achievement of CR, assuming that approximately 30% will achieve CR. We will also evaluate the TEML on achievement of CR or PR for at least 6 months. For the DLBCL and FL cohorts, we will evaluate each for the influence of TEML on achievement of response (~40-50%) using logistic regression analyses. For each of these cohorts, we will also assess the influence of TEML on PFS using Cox regression models and log-rank tests. Multivariable versions of these models will also be used to adjust for other clinical characteristics. Similar analyses will be used for evaluating the influence of specific mutations (dichotomized

measures) as well as GEP. We will use a log2 transformation of the GEP measures in our analyses, following standard practice for these types of expression measures. We will also evaluate the influence of immunologic markers on response and PFS for these different histology groups in a similar manner. Spatial markers will be assessed via a density measure of the different immune cell subsets and checkpoint molecules. Finally, we will also assess if there are meaningful cut-points for the TEML and other continuous measures that correspond with response or PFS using recursive partitioning algorithms. The influence of these resulting dichotomized markers will then be assessed in relation to the corresponding clinical outcomes.

Quantitative PET analyses: Quantitative PET parameters and their change over time will be summarized by various descriptive statistics. We will explore their association with clinical endpoints (complete response, overall response and PFS) using appropriate statistical tests (such as two-sample t-test and Wilcoxon rank sum test for analyses on response and log rank test for analyses on PFS) and regression analyses (logistic regression for response and Cox proportional hazards model for PFS).

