4.6.4 Rationale for Additional Patients in Expansion Cohort

Monotherapy with PD-1 blockade does not produce durable remissions in the great majority of patients with R/R HL. Therefore, effective therapies for patients with R/R HL who have prior exposure to PD-1 blockade is a major unmet need. Among the initial 42 patients enrolled onto the study, there were 15 patients with prior exposure to PD-1 blockade and the results were extremely promising with 13 out of 15 patients achieving an objective response. Therefore, we will enroll an additional 10 patients with R/R HL who have prior anti-PD-1/PD-L1 exposure to more adequately explore the safety and anti-tumor activity of pembrolizumab plus vorinostat in this unique population. In addition, to minimize heterogeneity among PD-1/PD-L1 exposed patients (some could be PD1/PD-L1-exposed but still sensitive) we narrowed the eligibility to PD-1/PD-L1 refractory to focus on this particular group of patients where there is a high unmet need.

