4.6.6 Rationale for Biomarker Research/Correlative Studies

Immunologic and genomic biomarkers have been associated with tumor response to immunotherapy, including checkpoint inhibitors like pembrolizumab. We propose to evaluate a series of exploratory immunologic and genomic correlatives to explore the association between each biomarker and response or resistance to combined pembrolizumab and vorinostat therapy. The correlative studies described below are exploratory in nature, and meant to be hypothesis-generating -they will not be powered for statistical significance. The below description is an anticipated rather than an exact list of studies that will be performed, as the investigators reserve the right to adjust the studies to be performed as techniques evolve and new data may become available that is relevant to the study agent and/or study population.

• Immunologic Biomarkers:

PD-L1 expression in tumor cells is a biomarker for response to anti-PD1 therapy in solid tumors.⁸⁹ PD-L1 expression has also been demonstrated in all HL patients tested who responded to PD-1 inhibition with pembrolizumab or nivolumab.^{13, 14} Furthermore, the pattern and spatial relationship between PD-1 and PD-L1-expressing cells are associated with response in patients with melanoma treated with pembrolizumab.²⁷

The presence, abundance, and composition of tumor infiltrating lymphocyte (TIL) populations in various tumor types are associated with clinical outcome.⁹⁰⁻⁹² In addition, the presence of certain TIL populations, particularly CD8+ T-cells, and their spatial orientation in tumors is associated with outcome after immunotherapy, including PD-1 blockade with pembrolizumab.^{27, 93} Using high-resolution spectral analysis and automated scanning of tissue sections, the [name] laboratory at City of Hope has developed a technique for quantitative, spatial IHC analysis of TIL and other immune cell subsets in a tumor. The [name] lab has demonstrated that spatial grouping patterns of TILs and dendritic cells differ between tumor-draining lymph nodes and normal lymph nodes and are associated with outcome in patients with breast cancer.^{94, 95}

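### Section 11.4 chooses biomarker cut-points from response or PFS, then assesses the dichotomised markers against those same outcomes with no correction for the search

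*Combined protocol and SAP*

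**What the plan says.** Section 11.4 (Correlative Studies) first analyses markers on their continuous scale: "logistic regression models will be used to evaluate the influence of TEML on whether or not patients responded to therapy", with Cox models and log-rank tests for PFS. Immunologic markers follow the same pattern by histology: "We will also evaluate the influence of immunologic markers on response and PFS for these different histology groups in a similar manner". A final step then looks for "meaningful cut-points for the TEML and other continuous measures that correspond with response or PFS using recursive partitioning algorithms", and the next sentence reads: "The influence of these resulting dichotomized markers will then be assessed in relation to the corresponding clinical outcomes".

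Section 4.6.6 says of the correlative studies that "they will not be powered for statistical significance", and section 11.4 itself labels them exploratory. Neither section states an alpha level, the partitioning algorithm, a minimum leaf size, a pruning rule or the test for the dichotomised marker. No hold-out set, cross-validation, bootstrap, permutation or adjusted p-value appears anywhere for this step.

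**The concern.** A cut-point found by searching for the best separation of an outcome will separate that outcome well even when the marker is noise. A conventional test then treats the cut as if it had been fixed in advance. It ignores the search, so the p-value is too small and the odds ratio, hazard ratio or response difference too large. That the same patients are used in both steps is an inference, but the documents describe no other patients and no division of the data.

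Nothing in the primary or secondary endpoints, the sample size or the stopping rule depends on this. What is at stake is the purpose of the correlative work, which is to decide which markers deserve further study. This step favours noise markers and shows them with exaggerated separation.

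**Working it through.** **The plan's own figures.** There is no stated error rate to reproduce. The only related figure is the sample size, "The expected sample size is 52 evaluable patients: 12 during the dose-escalation portion, and 40 patients in the expansion cohort": 12 + 40 = 52, which adds up.

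**Inputs from the documents**
- Outcome rates (section 11.4): "assuming that approximately 30% will achieve CR" for HL, and response of about 40 to 50% for DLBCL and FL. Rates of 0.30 and 0.45 were used.
- Cohort sizes are not stated by histology. Section 4.6.4 says "Among the initial 42 patients enrolled onto the study, there were 15 patients with prior exposure to PD-1 blockade" and adds 10 more HL patients. If those 15 all had HL (assumption), HL is at least 15 + 10 = 25. DLBCL plus FL is then at most 52 − 25 = 27, or about 13 each if split equally (assumption).

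**Assumptions not in the documents:** two-sided 5% test, one unpruned split of one marker, minimum leaf *m* of 3 to 7 patients, 30–50% censoring for PFS.

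**Method.** Simulate a marker unrelated to the outcome and order the *n* patients by it. Search every cut that leaves at least *m* per side, which is n − 2m + 1 cuts. At n = 25 that is 20 cuts for m = 3 and 12 for m = 7.

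For response, take the cut with the largest Gini reduction. For groups of size n₁ and n₂ with response rates p₁ and p₂, and overall rate p:
- Gini reduction = 2n₁n₂(p₁ − p₂)²/n²
- Pearson chi-square = n₁n₂(p₁ − p₂)²/[n·p(1 − p)]

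Within one data set *n* and *p* are fixed, so the algorithm picks the cut with the largest chi-square. For PFS, take the cut with the largest log-rank statistic (O − E)²/V. Then test the chosen cut at 5% as if pre-set. There were 6,000 replicates per response cell and 3,000 per PFS cell.

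**Share of noise markers with p<0.05** (response rate 0.45; 30% censoring)

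| n | leaf | cuts searched | Fisher | log-rank |
|---|---|---|---|---|
| 13 | 3 | 8 | 9.0% | 27.1% |
| 13 | 5 | 4 | 6.5% | 15.8% |
| 14 | 7 | 1 | 1.1% | 6.0% |
| 25 | 3 | 20 | 20.8% | 40.1% |
| 25 | 7 | 12 | 15.4% | 23.6% |
| 40 | 3 | 35 | 26.2% | 46.5% |
| 40 | 7 | 27 | 20.6% | 33.1% |

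At n = 25 and response rate 0.30, Fisher gives 18.1% (leaf 3) and 12.0% (leaf 7). With 50% censoring, log-rank gives 36.5% and 22.9%. A pre-set median split gives at most 4% for Fisher and 5–7% for log-rank. The n = 14, leaf 7 row allows only one cut, so there is no search and no inflation.

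A separate simulation with a minimum leaf of 10% of *n* (at least 3) gave, at n = 52, 27–29% for Fisher and 40% for log-rank. A logistic likelihood-ratio test on the chosen cut at n = 25 gave about 25–45%.

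**Effect size with no true effect.** At n = 25 the median response-rate difference at the chosen cut is 27–40 points, against 12–13 at a pre-set median split. In the separate simulation the median apparent odds ratio was about 5.5 (n = 17), 4.9 (n = 30) and 3.2 (n = 52).

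**Size of correction needed.** The unadjusted log-rank p-value that corresponds to a search-adjusted 5% is 0.0040 (n = 13, leaf 3), 0.0033 (n = 25, leaf 5) and 0.0015 (n = 40, leaf 5).

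**Check of the remedy.** A permutation p-value that repeats the whole search (199 permutations) gave false-positive rates of 3.4–4.8% for response and 5.2–6.5% for PFS (400 replicates, Monte Carlo standard error about 1.1 points) at n = 13–40. The separate simulation gave 3.6%, 4.3% and 3.7% for response at n = 17, 30 and 52.

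**The case against.** The strongest reply is that this is the last exploratory step of a phase I trial, already declared unpowered, and that the continuous-marker models come first. That stands, and it limits the importance of the point. It does not answer it: lack of power is about missing real effects, whereas this step manufactures false ones.

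Second, the plan asks whether meaningful cut-points exist, so finding none is allowed, and the simulation forces a split. This is partly right. With leave-one-out pruning (again an assumption), a split survived for about 19–26% of noise markers at n = 13–25. The Fisher rate at n = 25 fell from 12–21% to 9–16%, which is lower but still well above 5%. An algorithm that split only after a search-adjusted test would control the error of the split, but the plan does not specify one.

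Third, the assessment of the dichotomised markers could be purely descriptive. The wording permits that, but elsewhere in section 11.4 the influence of a marker is evaluated by logistic, Cox or log-rank analysis, so a formal test is the natural reading.

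Fourth, cohort sizes are uncertain, and in the smallest cohorts Fisher's test is near nominal. This is correct. The log-rank rate at n = 13 is nevertheless 16–27%.

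**Conclusion.** The concern holds. As written, section 11.4 selects the cut on the outcome and then assesses it on the same outcome without correction. P-values will be understated and effects overstated whenever more than one cut is searched. For a plausible HL cohort of 25, a noise marker would be nominally significant in about 12–21% of cases (Fisher) or 23–40% (log-rank); repeat runs put the log-rank range at 21–42%. At n = 40 with leaf 3 the log-rank rate reaches 46.5%. For Fisher's test with about 13 patients the inflation is slight.

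These rates depend on the assumed 5% level, leaf sizes, censoring and a single unpruned split, none of which the plan fixes. They are also per marker: ten independent markers tested properly at 5% already give 1 − 0.95¹⁰ = 40% for at least one false positive, before any cut-point search. The point should be corrected, but it does not threaten the trial's main conclusions.

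**What to change.** In section 11.4, state that the continuous-marker logistic and Cox models already planned carry the main inference. For each cut-point derived from the data, choose one of the following:

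- **Adjusted reporting.** Give a permutation p-value that repeats the whole split search, including any pruning, on each permuted outcome, together with a bootstrap- or cross-validation-corrected effect estimate.
- **Descriptive reporting.** Show the cut-point and the observed separation with no p-value, and say that it needs validation in other patients.

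Also name the partitioning algorithm, the minimum leaf size, the pruning rule and the test for the dichotomised marker.

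The cost is a few lines of code and a short change to the analysis plan. No new data or patients are needed. Exploratory p-values will look less favourable.
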